Research question and objectives	Following the initiation of any ARV regimen containing CAB and/or RPV LA among people living with HIV, the study will aim to assess usage patterns, durability, discontinuation, and virologic outcomes. Objectives: 1. Describe CAB and/or RPV LA containing regimens usage patterns 2. Assess adherence, durability and discontinuation of CAB+RPV LA regimen 3. Assess the clinical effectiveness (i.e. proportion of individuals experiencing virologic failure) among PLWH who are on CAB+RPV LA regimen 4. Monitor for resistance and next treatment response among individuals who switched off CAB+RPV LA (where data is available)		
Country(-ies) of study	Albania, Argentina, Austria, Belarus, Belgium, Bosnia & Herzegovina, Croatia, Czech Republic, Denmark, Estonia, Finland, France, Georgia, Germany, Greece, Hungary, Iceland, Ireland, Israel, Italy, Lithuania, Luxembourg, Netherlands, North Macedonia, Norway, Poland, Portugal, Romania, Russia, Serbia, Slovenia, Spain, Sweden, Switzerland, Ukraine, United Kingdom		
Author	PPD , MBBS, MPH, PhD PPD , Epidemiology & Real World Evidence ViiV Healthcare [name] Email: Phone:		

MARKETING AUTHORISATION HOLDER(S)

Marketing authorisation holder(s)	ViiV Healthcare B.V. [name]	
	Janssen-Cilag International N.V. [name]	
Person/Company authorised for communication on behalf of the MAH in the European Union	GlaxoSmithKline R&D GlaxoSmithKline R&D [name] Email PPD	

TABLE OF CONTENTS

1.	LIST OF ABBREVIATIONS	6
2.	RESPONSIBLE PARTIES: SPONSOR INFORMATION PAGE	9
3.	ABSTRACT	12
4.	AMENDMENTS AND UPDATES	15
5.	MILESTONES	15
6.	RATIONALE AND BACKGROUND 6.1. Background 6.2. Rationale	16
7.	RESEARCH QUESTIONS AND OBJECTIVE(S)	17
8.	RESEARCH METHODS 8.1. Study Design 8.2. Study Population and Setting 8.3. Clinical Variables 8.3.1. Exposure definitions 8.3.2. Outcome definitions 8.3.3. Confounders and effect modifiers 8.4. Study size 8.5. Data management 8.5.1. Data handling conventions 8.5.2. Timings of Assessment during follow-up 8.6. Data analysis 8.7. Quality control and Quality Assurance 8.8. Limitations of the research methods	18202124272727
9.	PROTECTION OF HUMAN SUBJECTS	32
10.	MANAGEMENT AND REPORTING OF ADVERSE EVENTS/ADVERSE REACTIONS	34
11.	PLANS FOR DISSEMINATING AND COMMUNICATING STUDY RESULTS	34 34

1. LIST OF ABBREVIATIONS

ADE	AIDS-defining Event		
AE	Adverse Event		
AIDS	Acquired Immunodeficiency Syndrome		
ALT	Alanine Aminotransferase		
AST	Aspartate aminotransferase		
ART	Antiretroviral Therapy		
ARV	Antiretroviral		
BCG	Bacillus Calmette–Guérin		
BMI	Body Mass Index		
CAB	Cabotegravir		
CD4	Cluster of Differentiation 4		
CD8	Cluster Differentiation 8		
CKD	Chronic Kidney Disease		
CRF	Case Review Form		
CVD	Cardiovascular Disease		
CVF	Confirmed Virologic Failure		
DAA	Direct-acting Antiviral		
DEXA	Dual-energy X-ray Absorptiometry		
DNA	Deoxyribonucleic Acid		
DUS	Drug Utilization Study		
EC	Ethics Committee		
eGFR	Estimated Glomerular Filtration Rate		
EMA	European Medicines Agency		
ESLD	End stage liver disease		
EU	European Union		
GI	Gastrointestinal		
GCP	Good Clinical Practice		
HbA1c	Haemoglobin A1c		
HBsAG	Hepatitis B Surface Antigen		
HBV	Hepatitis B Virus		
НСР	Healthcare Provider		
HCV	Hepatitis C Virus		
HDL	High Density Lipoprotein		
HICDEP	HIV Collaboration Data Exchange Protocol		
HIV	Human Immunodeficiency Virus		
IRB	Institutional Review Board		
INR	International Normalized Ratio		
INSTI	Integrase Strand Transfer Inhibitor		
IQR	Interquartile Range		
LA	Long Acting		
LAI	Long Acting Injectable		
LDL	Low Density Lipoprotein		
LOD	Limit of Detection		

MAH	Marketing Authorization Holder		
MI	Myocardial Infarction		
MTCT	Mother-to-Child Transmission		
NADM	Non-AIDS Defining Malignancies		
NNRTI	Non-Nucleoside Reverse Transcriptase Inhibitor		
PASS	Post Authorization Safety Study		
PCR	Polymerase Chain Reaction		
PLWH	Person Living with HIV		
PMTCT	Prevention of Mother-to-Child Transmission		
REDCap	Research Electronic Data Capture		
RNA	Ribonucleic Acid		
RPV	Rilpivirine		
QA	Quality Assurance		
SAE	Serious Adverse Event		
SARS-CoV-2	Severe Acute Respiratory Syndrome Coronavirus 2		
SmPC	Summary of Product Characterization		
SOP	Standard Operating Procedure		
STI	Structured Treatment Interruption		
TB	Tuberculosis		
VL	Viral Load		

Trademark Information

Trademarks of ViiV Healthcare and the GlaxoSmithKline group of companies
CABENUVATM
VOCABRIA™

Trademarks not owned by ViiV Healthcare and the GlaxoSmithKline group of companies	
REKAMBYSTM	
EDURANT™	

3. ABSTRACT

(a) Title with subtitles including version and date of the protocol and name and affiliation of the main author:

Drug Utilization, Adherence, Effectiveness and Resistance: A Prospective Observational Cohort Study in People living with HIV (PLWH) initiating ARV regimen CAB+RPV LA in Collaboration with EuroSIDA; v1.0; 26Jan2021; PPD , MBBS, MPH, PhD, Epidemiology & Real World Evidence, ViiV Healthcare

(b) Rationale and background:

Cabotegravir (CAB), a human immunodeficiency virus type-1 (HIV-1) integrase strand transfer inhibitor (INSTI), in combination with Rilpivirine (RPV), an HIV-1 non-nucleoside reverse transcriptase inhibitor (NNRTI), is indicated as a complete regimen for the treatment of HIV-1 infection in adults who are virologically suppressed (HIV-1 RNA <50 copies /mL) on a stable antiretroviral (ART) regimen without present or past evidence of viral resistance to, and no prior virological failure with agents of the NNRTI and INSTI class. Prior to the initiation of CAB long acting (LA) injection, CAB tablets together with RPV tablets should be taken for approximately one month (at least 28 days) to assess tolerability to CAB and RPV.

The Marketing Authorization Holder (MAH) proposes a five-year Drug Utilization Study (DUS) to be conducted in a real-world clinical setting. This prospective observational cohort study will aim to better understand the individual population receiving CAB and/or RPV LA containing regimens in routine clinical practice, usage patterns, adherence, post marketing clinical effectiveness of these regimens and monitor for resistance among virologic failures for whom data on resistance testing are available.

(c) Research question and objectives:

Following the initiation of any ARV regimen containing CAB and/or RPV LA among people living with HIV (PLWH), the study will aim to assess usage patterns, durability, discontinuation, and virologic outcomes.

- 1. Describe CAB LA and/or RPV LA containing regimens usage patterns
- 2. Assess adherence, durability and discontinuation for persons starting CAB+RPV LA regimen
- 3. Assess the clinical effectiveness (i.e. proportion individuals experiencing virologic failure) among PLWH who initiate CAB+RPV LA regimen)
- 4. Monitor for resistance and next treatment response among individuals who switched off CAB+RPV LA regimen, where VL data are available and resistance testing has been done as part of routine clinical practice

5. Evaluate the effectiveness of routine risk minimisation measures for regimen adherence, discontinuation due to incorrect route of administration and off-label use of CAB+RPV LA regimen

(d) Study design:

This post authorization safety study (PASS), a non-interventional prospective observational cohort study will be nested within the EuroSIDA study, using data from individual medical records from participating clinical sites will be conducted over a period of five years to meet the study objectives.

(e) Population:

The study population will include PLWH over the age of 18 years, from EuroSIDA clinical sites who are new users of CAB and/or RPV LA containing regimens over a period of 5 years. Persons will be eligible for inclusion from the date of starting the treatment regimens after approval and commercial availability of the regimens.

(f) Variables:

The EuroSIDA study collects a comprehensive range of data including demographics, infection-related laboratory data, other laboratory data, antiretroviral start and stop dates and reasons for discontinuation, paraclinical and clinical events.

(g) Data sources:

EuroSIDA is a well-established, prospective observational cohort study of more than 13,000 individuals under active follow-up in over 100 hospitals in 34 European countries, and Israel and Argentina. Following the approval and commercial availability of CAB+RPV LA, the study will collect prospective data on individuals initiating CAB and/or RPV LA containing regimens, over the course of 5 years.

(h) Study size:

Sample size will depend on the market uptake of CAB and/or RPV LA following its commercial availability in European countries. Based on possible uptake of CAB+RPV LA and rates of discontinuation or virologic failure, the likely precision of the estimates can be determined using Exact Clopper Pearson confidence limits under different scenarios.

(i) Data analysis:

Descriptive analyses will summarize the study population exposed to CAB and/or RPV LA. Discontinuations of CAB+RPV LA will be summarized and logistic regression will be used to identify factors associated with missing 1 or more dose and receiving an injection 7 or more days late. Multivariable logistic regression models will investigate the factors associated with virologic failure at 6 months, 12 months and 24 months after CAB+RPV LA initiation and resistance patterns presented for those with resistance data available.

(j) Milestones:

The study will start after the protocol is approved by the EMA, and CAB+RPV LA is registered and commercially available in the relevant countries and is expected to continue through 2026 or later, for a total of five years of study period. Annual interim reports with cumulative data will be submitted and a final report is expected to be submitted in September 2026.

4. AMENDMENTS AND UPDATES

Amendment or update no	Date	Section of study protocol	Amendment or update	Reason

5. MILESTONES

Milestone	Planned date
Draft Protocol Submission	Dec 31, 2020
Study Start (Protocol Approval)	Estimated - June 2021
1st Interim Report	Draft -Dec, 2022
_	Final- Mar, 2023
2 nd Interim Report	Draft -Dec, 2023
	Final- Mar, 2024
3 rd Interim Report	Draft -Dec, 2024
	Final- Mar, 2025
4 th Interim Report	Draft -Dec, 2025
	Final- Mar, 2026
Data Collection Completion	June 2026 or 5 years following
_	commercial availability of CAB
Final Report	Sep 2026
Supplemental Report	Depends on when the last individual
_	discontinuing the CAB+RPV LA
	regimen completes 4-years of follow up

6. RATIONALE AND BACKGROUND

6.1. Background

Cabotegravir (CAB), a human immunodeficiency virus type-1 (HIV-1) integrase strand transfer inhibitor (INSTI), in combination with Rilpivirine (RPV), an HIV-1 non-nucleoside reverse transcriptase inhibitor (NNRTI), is indicated as a complete regimen for the treatment of Human Immunodeficiency Virus type 1 (HIV-1) infection in adults who are virologically suppressed (HIV-1 RNA <50 copies/mL) on a stable antiretroviral (ART) regimen without present or past evidence of viral resistance to, and no prior virological failure with agents of the NNRTI and INSTI class. Prior to the initiation of CAB long acting (LA) injection, CAB tablets together with RPV tablets should be taken for approximately one month (at least 28 days) to assess tolerability to CAB and RPV.

Treatment with CAB+RPV LA should be prescribed by a physician experienced in the management of HIV infection. Each injection should be administered by a healthcare provider (HCP). Prior to starting the regimen, the HCP should carefully select individuals who agree to the required injection schedule and counsel individuals about the importance of adherence to scheduled dosing visits to help maintain virologic suppression and reduce the risk of viral rebound and potential development of resistance associated with missed doses. Following discontinuation of CAB+RPV LA injection, it is essential to adopt an alternative, fully suppressive ARV regimen per the summary of product characterization (SmPC).

The Marketing Authorization Holders (MAH) propose a five-year Drug Utilization Study (DUS) to be conducted in a real-world clinical setting. This prospective observational cohort study will aim to better understand the individual population receiving CAB and/or RPV LA containing regimens in routine clinical practice, usage patterns, adherence, post marketing clinical effectiveness of these regimens and monitor for resistance among virologic failures for whom data on resistance testing are available.

6.2. Rationale

There is a need to understand the CAB and/or RPV LA containing regimens utilization in a real-world clinical setting. Adherence to scheduled dosing visits to help maintain viral suppression and reduce the risk of viral rebound and potential development of resistance with missed doses is critical for long term maintenance of viral suppression. Impact of non-adherence on virologic failure and emergence of resistance need to be assessed in a real world clinical setting among a more heterogeneous population than often represented in clinical trials.

7. RESEARCH QUESTIONS AND OBJECTIVE(S)

Following the initiation of any ARV regimen containing CAB and/or RPV LA among PLWH, the study will aim to assess usage patterns, durability, discontinuation, and virologic outcomes.

The specific objectives are to:

- 1. Describe CAB and/or RPV LA containing regimens usage patterns
 - Descriptive analysis of study population by baseline demographic and clinical characteristics
 - Monitor for use of oral lead-in
 - The potential regimen combinations are listed below (Note that CAB+RPV LA is the only approved regimen)
 - a. CAB+RPV LA regimen only
 - b. CAB LA monotherapy
 - c. CAB LA use in combination with ARVs other than RPV LA
 - d. RPV LA monotherapy
 - e. RPV LA use in combination with ARVs other than CAB LA
 - f. CAB LA+RPV LA+other ARVs
 - g. Combined group b-f
- 2. Assess adherence, durability and discontinuation for persons starting CAB+RPV LA regimen;
 - Proportion of individuals discontinuing the regimens of interest will be assessed.
 - Reasons for discontinuation will be assessed.
 - Non-adherence to the dosing schedule will be assessed by:
 - a. Estimating the number of individuals that missed one or more consecutive injections without taking daily oral bridging therapy or any other oral ARV regimen while not on CAB+RPV LA containing regimens and mean and median number of injections missed during a 12-month period
 - b. Estimating the number of individuals who received the injections seven or more days later than their scheduled injection visit and median duration of delayed injections
 - c. Estimating the number of individuals who missed one or more consecutive injections without taking daily oral bridging therapy or those who received the injections seven or more days later than their scheduled injection visit (Combined group a OR b) and describe patient characteristics for the individuals that are nonadherent.
 - Number of individuals with incorrect route of administration will be described.

- 3. Assess the clinical effectiveness (i.e. proportion of individuals experiencing virologic failure) among PLWH who initiate CAB+RPV LA regimen
 - a. Estimate the proportion of individuals with virologic failure, during the first 6 months after initiation of CAB+RPV LA
 - b. Estimate the proportion of individuals with virologic failure, at 6, 12 and 24 months after initiation of CAB+RPV LA
 - c. Stratified analyses for 3a and 3b will be conducted for VL at regimen initiation (<50 copies/mL and ≥50 copies/mL).
 - d. Assessment of VL for PLWH on other regimen combinations (b-f in objective 1) at 6, 12 and 24 months after initiation of the regimen
- 4. Monitor for resistance and next treatment response among individuals who discontinued CAB+RPV LA, where VL data are available and resistance testing has been done as part of routine clinical practise
 - Describe the ARV regimen individuals are switched to after discontinuation of CAB+RPV LA containing regimens
 - Monitor for resistance (where this has been done as part of routine clinical practise) during the 48 months following the switch
 - Describe virologic outcomes at 12, 24, 36 and 48 months after discontinuation of CAB+RPV LA containing regimens
- 5. Evaluate the effectiveness of routine risk minimisation measures for regimen adherence, discontinuation due to incorrect route of administration and off-label use of CAB+RPV LA regimen
 - Assess off-label use as described in objective 1
 - Estimate proportion of treatment naive or individuals not suppressed initiating regimen
 - Assess non-adherence to the dosing schedule as described in objective 2
 - Assess the frequency of discontinuation due to incorrect route of administration

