8.3.2. Outcome definitions

1.Regimen discontinuations: Discontinuation of CAB+RPV LA regimen for any reason during the study period will be captured, tabulated and reported.

Individuals who receive the oral lead-in but never initiate the CAB+RPV LA regimen will be tabulated separately but not included in the primary analysis.

Discontinuation of CAB +RPV LA will be defined as the latest date of the next scheduled injection which is missed and where bridging therapy has not been started. For example, for monthly dosing, if the first injection of CAB+RPV LA was received on June 1st, the second injection should be received on July 1st (allowed time window for second injection is June 24th to July 8th). The third injection should follow the timing of the first injection and should be received on August 1st (allowed time window for third injection is July 25th to August 8th). If not, date of discontinuation will be defined as August 8th (Monthly dosing).

For every 2 month dosing, if the first injection of CAB+RPV LA was received on June 1st, the second injection should be received on July 1st (allowed time window for second injection is June 24th to July 8th). The third injection should follow the timing of the first injection and should be received on September 1st (allowed time window for third injection is August 25th to September 8th). If not, date of discontinuation will be defined as September 8th (Every 2 month dosing).

Discontinuation will also be captured, tabulated and reported for any other CAB and/or RPV containing regimen.

Durability will be measured as proportion of individuals continuing on the regimen at the end of 6, 12 and 24 months.

Adherence will be assessed by estimating the number of individuals that missed one or more consecutive injections without taking daily oral bridging therapy or any other oral ARV regimen while not on CAB+RPV LA regimen and mean and median number of injections missed during a 12-month period. We will also estimate the number who received the injections seven or more days later than their scheduled injection visit and median duration of delayed injections in persons using bridging therapy.

In the standard follow-up data collection in EuroSIDA reasons for discontinuation are recorded as below.

Table 3. EuroSIDA – Reasons for Treatment Discontinuation

Code	Reason for Stopping Treatment
1	Treatment failure (i.e. virological, immunological, and/or clinical failure
1.1	Virological failure

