Non-adherence to dosing schedule will be assessed by estimating the number of individuals that missed one or more consecutive injections without taking daily oral bridging therapy or any other oral ARV regimen while not on CAB+RPV LA regimen and median number of injections missed during a 12-month period. We will also estimate the number who received the injections seven or more days later than their scheduled injection visit and median duration of delayed injections in persons using bridging therapy. In addition, the number of individuals who missed one or more consecutive injections without taking daily oral bridging therapy or those who received the injections seven or more days later than their scheduled injection visit will be assessed and patient characteristics for those individuals that are non-adherent will be described.

Logistic regression will be used to identify factors associated with not starting CAB+RPV LA in those that start lead in, to compare those missing injections where bridging treatment is used, non-adherence and to identify factors associated with discontinuation of CAB+RPV LA (when there are more than 30 endpoints). Potential explanatory variables are listed above. The model building strategy will follow EuroSIDA protocol and include variables significant in univariate analyses as well as *a priori* pre-specified variables of interest.

AIM 3. Assess the clinical effectiveness (i.e. proportion individuals experiencing virologic failure and proportion with undetectable VL) among PLWH who initiate CAB+RPV LA regimen

The study will estimate the proportion with virologic failure during the first six months and at six, twelve and twenty four months after the start of the treatment with injectable regimen. Given that this study involves persons in routine clinical care, and who may not attend clinic appointments at 6, 12 or 24 months, a window of 12 weeks around the date in question will be used for virologic failure. Thus, the proportion with virologic failure during first six months, at 6, 12 or 24 months \pm 6 weeks will be used; and if none is available, the first measurement during first six months, after 6, 12 or 24 months (and at most 6 weeks after the measurement).

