case of resumption of LAI after missed second injection in two months or less, we will still consider it first exposure.

Similarly, the third injection (and injections thereafter) for the two-month schedule is given two months after the second injection and hence we will allow four months after the second injection to see if the regimen was resumed (≤3 months) or re-initiated (>3 months). In case of resumption of LAI after missed third injection in three months or less, we still consider it first exposure.

Treatment with long-acting antiretroviral therapy

Which long-acting antiretroviral drugs have been initiated? (drop down menu)

1) long acting cabotegravir + long acting rilpivirine

2) long acting cabotegravir without rilpivirine

3) long acting rilpivirine without cabotegravir

Dosage: 400/600 mg (CAB) / 600/900 mg (RPV) (drop down

menu)

Date of first injection: Year/month/day

Intended dosing schedule of long-acting antiretroviral therapy Monthly/Every 2 Month

HIV resistance testing (only pops up for the first injection and if CAB + RPV has been selected)

Has a HIV resistance test been performed prior to initiation of long-acting cabotegravir + rilpivirine yes/no

If yes

Date of latest most recent resistance test prior to initiation of long-acting antiretroviral therapy Year/month/day

Method used drop down menu

Please upload a copy of the resistance test report (result will be based on central review)

(After completion of date of first injection, a new section will open for second injection with target date one month after the first injection. All the questions below refer to subsequent injections after the first)

Has the patient received the next planned injection with long-acting antiretroviral drugs yes/no

If yes, Which long-acting antiretroviral drugs were given? (drop down menu)

1) long acting cabotegravir + long acting rilpivirine

2) long acting cabotegravir without rilpivirine

3) long acting rilpivirine without cabotegravir

Dosage: 400/600 mg (CAB) / 600/900 mg (RPV) (drop down

menu)

Date of injection: Year/month/day

Intended dosing schedule of long-acting antiretroviral therapy Monthly/Every 2 Month

(if the patient switches from monthly to two-monthly injections or vice versa, a new question pops up)

Reason for switching to monthly (or 2 monthly) injection schedule (drop down menu)

- 1. Convenience
- 2. To reduce cost
- 3. To reduce side effects
- 4. Personal reasons
- 5. Other (+ text field)

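### The non-adherence definitions conflict with the protocol's own injection window and discontinuation rule, and the per-person counts ignore that monthly users have twice as many scheduled injections

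*Protocol*

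**What the plan says.** **Non-adherence (Section 7, objective 2).** Part a counts persons who "missed one or more consecutive injections without taking daily oral bridging therapy or any other oral ARV regimen" while off the long-acting regimen. Part b counts those who "received the injections seven or more days later than their scheduled injection visit and median duration of delayed injections", with no exemption for bridging. Part c joins un-bridged misses to "those who received the injections seven or more days later than their scheduled injection visit (Combined group a OR b", again with no exemption on the late limb.

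**Window (Section 8.3.2).** For a July 1st target, the "allowed time window for second injection is June 24th to July 8th". The August 1st and September 1st examples have the same shape, and Annex 1 gives ±7 days.

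**Discontinuation (Section 8.3.2).** If the injection is not given by the last day of the window and bridging has not started, the person is discontinued on that day. Annex 1, for the two-month schedule, still treats resumption within two months (second injection) or three months (later injections) as first exposure.

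**Delay length.** Sections 8.3.2 and 8.6 (Aim 2) report the "median duration of delayed injections in persons using bridging therapy". Objective 2b has no such restriction.

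**Risk factors.** The Abstract states that "logistic regression will be used to identify factors associated with missing 1 or more dose and receiving an injection 7 or more days late", and Section 8.6 plans logistic regression for non-adherence. Annex 1 records "Intended dosing schedule of long-acting antiretroviral therapy Monthly/Every 2 Month", but the variables in Section 8.3.3 do not include dosing schedule.

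**The concern.** Adherence is in the study title, is objective 2, and is reused in objective 5 to judge routine risk minimisation, by region (Section 8.6, Aim 5). Missed and delayed doses are also explanatory variables for resistance (Aim 4). If one injection can be in window and late, or exempt in one part of the measure and counted in another, the reported number depends on which section the analyst follows.

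The second issue is opportunity. An ever-late outcome per person rises with the number of injections scheduled. If schedule is left out of the model, factors that go with schedule, such as region or calendar time, can pick up part of that difference.

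**Working it through.** **1. Window against lateness threshold.** July 8th minus July 1st, August 8th minus August 1st and September 8th minus September 1st are each +7 days; the lower limits are each −7 days. The window therefore includes day +7, and the late rule starts at day +7. The overlap is that single day; days −7 to +6 are unaffected.

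**2. Three cases under the stated rules.** These use the two-monthly example in Section 8.3.2: first injection June 1st, second July 1st, third due September 1st. September 20th is chosen for illustration and is 19 days after the target.

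| Third injection | 2a | 2b | 2c | Delay length, Section 7 | Delay length, 8.3.2/8.6 | Status |
|---|---|---|---|---|---|---|
| September 8th, no bridging | no | late, 7 days | yes | in | out | in window, on regimen |
| September 20th, bridged | exempt | late, 19 days* | yes* | in* | in | on regimen |
| September 20th, un-bridged | yes, if the planned injection counts as missed | late, 19 days | yes | in | out | discontinued September 8th (8.3.2); still first exposure (Annex 1) |

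*If the original target date stays the reference. Annex 1 ties the target to the start date only while injections are given on schedule, so this is a possible reading and not the only one.

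Read strictly, Section 8.3.2 removes the third case from the regimen on September 8th. A person still on the regimen can then be late only on day +7 exactly or after bridging.

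**3. Opportunity.** Scheduled injections after the first, from the timings in Section 8.3.2 and Annex 1:

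- Monthly: months 1, 2, …, 12, which is 12.
- Two-monthly: months 1, 3, 5, 7, 9, 11, which is 6.
- At 24 months: 24 against 12. The ratio is exactly 2.

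Assume (not in the documents) the same lateness probability p for each injection in both schedules, independence, and full 12-month follow-up. Then P(ever late) = 1 − (1 − p)^k. With s = (1 − p)^6, the odds ratio is [(1 − s²)/s²] ÷ [(1 − s)/s] = 1 + 1/s.

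| p | Monthly (k = 12) | Two-monthly (k = 6) | Odds ratio |
|---|---|---|---|
| 0.5% | 5.8% | 3.0% | 2.03 |
| 1% | 11.4% | 5.9% | 2.06 |
| 2% | 21.5% | 11.4% | 2.13 |
| 3% | 30.6% | 16.7% | 2.20 |
| 5% | 46.0% | 26.5% | 2.36 |
| 10% | 71.8% | 46.9% | 2.88 |

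At 24 months with p = 2%: 38.4% against 21.5%, odds ratio 2.27. Late injections divided by scheduled injections gives p in both schedules, ratio 1.0.

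**4. Size of the day +7 overlap.** If a share of injections falls exactly on day +7 (assumed 0.5%, 1% or 2%), the same formula gives 3.0%, 5.9% or 11.4% of two-monthly users and 5.8%, 11.4% or 21.5% of monthly users labelled late within 12 months for an in-window injection alone.

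**The case against.** Several points on the other side stand.

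- The measure concerns adherence to the injection schedule, not drug cover. A bridged person injected late did depart from that schedule, and parts a and b are reported separately. That defends counting bridged delays somewhere; it does not explain why part a exempts them and part c, which combines a and b, can count them again.
- A reader might infer that un-bridged delays are lost because Sections 8.3.2 and 8.6 give delay length for bridged persons only. The documents do not support that: under Section 8.3.2 such persons are recorded as discontinued, and if the injection counts as missed they are also in 2a. What remains is the mismatch with 2b and with Annex 1's first-exposure rule.
- A reader might infer that on-time patients are generally labelled late. Only day +7 is affected, and nothing in the documents says how many injections fall there.
- A reader might take an odds ratio of about 2 as a false risk factor that the study will report. Schedule is not in the planned list, so no such coefficient would appear. Leakage into region or start date, which are listed, is smaller and cannot be quantified. If one schedule dominates, it largely disappears.
- Ever late per person is a legitimate utilisation measure, and Section 8.6 allows variables specified a priori, so an analysis plan could add schedule or a per-injection rate. It could not resolve the threshold, bridging and delay-length conflicts without departing from one protocol section or another.

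**Conclusion.** The concern holds as a set of contradictions in the protocol's own definitions, plus one uncontrolled source of variation. The contradictions need no assumption: day +7 is both in window and late; bridging exempts a person in 2a but not in the late limb of 2b and 2c; the population for delay length differs between Section 7 and Sections 8.3.2 and 8.6; and an un-bridged late resumption is a discontinuation in Section 8.3.2 but can remain first exposure in Annex 1.

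The twofold difference in scheduled injections is exact. Its effect on the ever-late odds ratio, about 2.0 to 2.9 at 12 months, rests on equal and independent lateness of 0.5% to 10% per injection and describes schedule itself. The distortion of other factors depends on the schedule mix, which is unknown. The point should be corrected, but the documents do not show that the study's adherence results as a whole would be unusable.

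**What to change.** Reconcile Section 7 (objective 2), Section 8.3.2, Section 8.6 (Aim 2) and Annex 1:

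1. For analysis, place each scheduled injection in one of four mutually exclusive categories: in window; late with bridging; late without bridging but resumed; discontinued. Classify day +7 the same way throughout. The clinical window itself is not changed.
2. In 2c, report bridged delays separately from un-bridged non-adherence. Give delay length for all late injections, split by bridging.
3. Add intended dosing schedule to the Section 8.3.3 variables.
4. Report late or missed injections per scheduled injection, or by schedule, alongside the per-person counts.

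Simply redefining late as after the window and not bridged would not do: that is the Section 8.3.2 discontinuation rule, so late and discontinued would merge. The four categories avoid this only if the Section 8.3.2 rule and Annex 1's resumption rule are reconciled first.

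The cost is wording and analysis code. Injection dates, bridging and schedule are already collected in Annex 1.
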